5.5.2.3. Rationale for Control Groups

Placebo Control Group

The use of a randomized placebo control group added to established standard of care provides the best scientific evidence of efficacy and safety. The use of a placebo control provides a concurrent comparator group, accounting for not only a placebo effect but a standard of care effect. Notably, accounting for the standard of care effect is critical when designing an outcome-based study conducted globally when there are regional differences in the treatment of subjects with PBC.

Historical Control Group

The available robust historical PBC observational datasets (UK-PBC and Global PBC Study Group) will also be leveraged to provide further comparative evaluation of the clinical benefit of OCA. Each database includes >6000 patients with long-term follow-up.

Comparison of OCA treatment to the historical controls may provide utility in addressing potential bias or confounds associated with the placebo arm. For example, bias associated with the potential addition of commercial OCA and/or differences in long-term standard of care between the treatment arms including ancillary treatments and diagnostics.

Therefore, further evaluation of the effect of OCA will compare OCA treatment versus historical controls, and will be supportive to placebo comparisons (ie, comparisons to historical and placebo controls will be evaluated separately).

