13.1.1.1. Comparability of Historical Controls

Utilization of both historical control/observational databases (UK-PBC and Global PBC Study Group), with more than 6000 subjects each, allow for a rigorous subject level meta-analysis. The historical databases include long-term follow up, detailed subject-level information such as baseline clinical characteristics, longitudinal liver biochemistry, and long-term outcomes, and span a broad range of subject characteristics that may influence disease (disease state, age, gender, and regional differences in standard of care). Historical controls from both databases will be chosen based on the same study inclusion/exclusion criteria. Propensity score matching method will be utilized to select historical controls that match the treated subjects using available covariates. The adequacy of matching will be assessed by statistical methods described under [Section 13.1.8](#).

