13.1.2. Determination of Sample Size

The target population is subjects who are at higher risk of liver-related clinical complications. Eligible subjects will have a diagnosis of PBC with bilirubin levels $>ULN$ and $\leq 5x ULN$ and/or $ALP > 3 \times ULN$. The following assumptions were used in sample size calculations:

- Exponential survival curves, placebo survival estimate of 0.6 at 8 years with a hazard ratio of 0.60, and total study duration of 10 years (from first subject enrolled), allowing for 4 years of subject accrual and 6 years of follow up.
- Subjects will be randomized in a 1:1 ratio to placebo or OCA.
- The 2 groups will be compared using a 2-sided log rank test at the 5% level of significance.
- Two interim analyses and one final analysis are planned. The first interim analysis will be performed when 50% of the target events are accrued and the second interim will be performed when 75% of the target events are accrued.
- A dropout rate of 10% is assumed

Based on the randomization ratio, significance level, and assumed hazard ratio, a total of 127 events (both groups combined) will provide 80% power to demonstrate a statistically significant difference between OCA and placebo on time to liver-related outcomes, including all-cause mortality.

In addition, based on the remaining assumptions stated above, it is estimated that approximately 428 subjects will be enrolled to attain 127 events.

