13.1.8. Supportive Analysis

Per the International Conference on Harmonisation (ICH) E10 guidance, “where no obvious single optimal external control exists, it may be advisable to study multiple external controls”. In order to address the risks associated with the inclusion of a long-term placebo arm, supportive analyses of the primary endpoint will compare clinical outcomes in the OCA treatment arm to historical controls, which serves as an external control for supportive analysis.

In an attempt to avoid the inherent biases with historical controls and to maintain the integrity of this comparison, one can invoke matching methods to optimize comparability and find a historical control that is “similar” to a participating subject. The historical database control should be as similar as possible to the study population and should have been exposed to a similar standard of care (see [Section 5.5.2.3](#)).

A propensity score can be used to reduce bias through matching, stratification, regression adjustment, or some combination. Propensity scores use information from a pool of patients who do not participate in the study (historical controls) to identify what would have happened to participating subjects in the absence of the treatment. By comparing how outcomes differ for treated subjects relative to historical controls, it is possible to estimate the effects of the treatment between the treated subjects and the matched natural history subjects.

A full range of covariates across which the treatment and historical controls might differ will be considered to mitigate potential bias. Although the results of using matching controls are conditional only on the observed covariates, if one has the ability to measure many of the covariates that are believed to be related to the treatment assignment, then one can be fairly confident that approximately unbiased estimates for the treatment effect can be obtained. Both UK-PBC Group and the Global PBC Study Group formally collect numerous covariates that could be used for propensity score estimation including standard of care, eg, UDCA.

Historical controls will be chosen based on the same inclusion/exclusion criteria where possible. Propensity scores will be estimated using the available covariates that predict receiving the treatment. Only covariates and not outcome variables will be included in the propensity score estimation, to avoid biased results that are in favor of one treatment.

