KM estimates of the distribution of the time-to-event will be tabulated and graphed by treatment group. The tabulation will include the KM estimate of the medians and corresponding 95% CIs if the medians can be estimated. The number and percent of subjects censored and with events will be presented. The hazard ratio and 95% CI will be determined based on a Cox regression model stratified by randomization strata to estimate the magnitude of the effect.

Sensitivity analyses will be conducted limiting to the separate individual historical control databases, ie, UK-PBC Group and Global PBC Study Group. To evaluate the robustness of the propensity score estimations, additional algorithms and factors may be considered.

Although the study is designed as a placebo-controlled study, the DMC may recommend changes to study conduct based on the pre-specified interim analyses (see [Section 13.1.12](#)), including the potential use of a revised primary efficacy analysis. This analysis would compare all subjects in the OCA population, to all control subjects (randomized placebo and historical controls) on time to liver transplant or death (all-cause), using similar statistical methodology as specified above.

Notably, the planned primary analysis would not be revised without prior agreement with regulatory authorities.

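### The contingent revised primary analysis pools randomized placebo with historical controls, and no check is planned that would show whether the two groups have the same outcome rate

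*Protocol*

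**What the plan says.** The planned primary analysis (Protocol 13.1.3) compares randomized OCA with randomized placebo. Historical controls are introduced as supportive: Section 5.5.2.3 states that "comparisons to historical and placebo controls will be evaluated separately".

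Section 13.1.8 then describes a fallback. After an interim analysis the DMC may recommend a revised primary analysis that would "compare all subjects in the OCA population, to all control subjects (randomized placebo and historical controls" on time to liver transplant or all-cause death, using methods similar to those of the supportive analysis. The section adds that regulators must agree first.

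Two passages govern which historical patients qualify. Section 13.1.1.1: "Historical controls from both databases will be chosen based on the same study inclusion/exclusion criteria". Section 13.1.8: "Historical controls will be chosen based on the same inclusion/exclusion criteria where possible". Section 13.1.1 also limits the historical populations to patients shown to be comparable with trial subjects in both characteristics and disease progression.

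The adjustment is propensity matching plus a log-rank test stratified by propensity quintile. The stated checks are Wilcoxon tests, standardized differences and variance ratios for baseline covariates, and box plots of the propensity scores. The Cox hazard ratio in 13.1.8 is stratified by the randomization strata; propensity strata are not mentioned for it.

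**The concern.** Matching and stratification on a propensity score remove differences in what was measured. Section 13.1.8 itself concedes that the results depend on the observed covariates. Period, care, and conditions bearing on all-cause death that the databases may not record can leave the historical patients with a different hazard from comparable placebo subjects. Once the two groups are merged, that difference becomes part of the estimated OCA effect, in what would then be the trial's primary result.

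The protocol sets itself the right standard, comparability in disease progression, but names no check that looks at progression or outcome. The trial holds the data for one. The randomized placebo arm met the full eligibility criteria and can be compared with the historical controls by the method already planned for OCA. Section 13.1.8 does not plan that comparison; the fallback pools the two groups instead.

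**Working it through.** **The plan's own figures.** Section 13.1.2 gives a "2-sided log rank test at the 5% level of significance", a "placebo survival estimate of 0.6 at 8 years with a hazard ratio of 0.60", and states that "a total of 127 events (both groups combined) will provide 80% power to demonstrate a statistically significant difference".

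- Freedman events: (1.96 + 0.842)² × (1.6/0.4)² = 7.849 × 16 = 125.6, so 126. Schoenfeld: 4 × 7.849 / (ln 0.6)² = 120.3, so 121 for a fixed design. With Lan-DeMets O'Brien-Fleming looks at 64, 96 and 127 events, power is 81.3%.
- Subjects: placebo hazard −ln(0.6)/8 = 0.0639 per year. With the timing stated ("allowing for 4 years of subject accrual and 6 years of follow up"), the average event probability is 0.331. Then 127/0.331 = 384, and 384/0.9 = 427, against 428 stated.

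These figures reproduce. They concern the composite endpoint against randomized placebo. Nothing is stated for the pooled analysis.

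**Assumptions for the pooled analysis.** The 8-year risk of transplant or death is 20% on placebo, so the hazard is −ln(0.8)/8 = 0.0279 per year. OCA and placebo have 214 subjects each and identical outcomes. There are h historical controls per OCA subject, with hazard r times placebo after propensity adjustment. Follow-up is 6 to 10 years (mean 8) with 10% dropout. None of the 20%, r or h comes from the protocol. Each database holds more than 6000 patients, so h above 1 is feasible.

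**Hand calculation, r = 1.3, h = 1.**

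- OCA events: 214 × 0.20 × 0.9 = 38.5. Placebo events: the same.
- Historical events: 214 × (1 − exp(−0.0279 × 1.3 × 8)) × 0.9 = 214 × 0.252 × 0.9 = 48.5. Pooled control events: 87.0.
- Average control hazard relative to placebo: (1 + 1.3)/2 = 1.15, so the apparent OCA hazard ratio is 1/1.15 = 0.87.
- Standard error of the log hazard ratio: √(1/38.5 + 1/87.0) = 0.194. Shift in z: ln(1.15)/0.194 = 0.72.
- Chance of significance favouring OCA: Φ(−1.96 + 0.72) = Φ(−1.24) = 11%. Nominal is 2.5%.

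**Log-rank simulation, same assumptions, significant results favouring OCA.**

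| Residual ratio r | h = 1 | h = 4 |
|---|---|---|
| 1.0 | 2.2% | 2.4% |
| 1.2 | 6% | 12% |
| 1.3 | 10% | 23% |
| 1.5 | 21% | 52% |

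For 8-year risks of 15-25%, r = 1.3 gives about 9-12% (h = 1) and 19-28% (h = 4).

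**The other direction.** A separate simulation used half the planning hazard, an 8-year risk of 1 − √0.6 = 22.5%. With r = 0.8 the apparent hazard ratio of an inactive drug is 1.12 (h = 1) or 1.18 (h = 3), and significant results favouring OCA fall to 0.5% or less. A real benefit would be masked to the same degree.

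OCA against randomized placebo alone does not involve r, so it keeps 2.5% throughout.

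**The case against.** The strongest reply is that this analysis is a gated contingency. It needs a DMC recommendation and prior regulatory agreement, and 13.1.12 repeats that gate for any modification of the study. That stands, and it limits the weight of the point. It does not supply the missing check: regulators would be asked to agree with nothing in the listed analyses showing whether placebo and historical outcomes match.

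Measured differences are also well handled. There is matching, quintile stratification, standard of care among the available covariates, an independent statistician for the matching, and sensitivity analyses by database. Only what remains after all this matters, and r above is defined that way.

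A reader might infer that the eligibility criteria are applied only in part, so that sicker historical patients would manufacture an OCA effect. The documents do not support this. The summary of changes from Version 3 to Version 4 shows the qualifier being taken out of 13.1.1.1, so its survival in 13.1.8 may be leftover wording. Nothing says that any criterion cannot be applied in the databases, or that r would exceed 1.

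It can also be said that OCA against placebo and OCA against historical controls are both already planned on transplant or death, so a reader could set them side by side. That is an indirect comparison with no interval of its own. Finally, placebo subjects who start commercial OCA would distort a placebo-versus-historical comparison. This is true and has to be stated with the result.

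**Conclusion.** The point holds in a limited form. Section 13.1.8 permits a pooled primary comparison that conflicts with the separation stated in 5.5.2.3, and the protocol requires comparability in disease progression without naming any check of it. A residual hazard difference would bias the pooled result in either direction. Under the stated assumptions the chance of a false OCA win is about 6-21% with one historical control per OCA subject and 12-52% with four, for r of 1.2 to 1.5; it falls below 2.5% when r is below 1. The upper figures combine the largest assumed r with the larger assumed control pool.

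A reader might conclude that the pooled analysis must be struck out and replaced by OCA against placebo only. That goes further than the documents require. The comparison on transplant or death is already a key secondary endpoint (13.1.4), and historical controls are there partly to address commercial OCA use in the placebo arm. Whether to pool is a trade-off; pooling without looking at the placebo-historical difference is the defect.

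**What to change.** In 13.1.8:

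- Add a comparison of randomized placebo with historical controls on each listed outcome, in the same propensity strata, reported beside OCA versus historical controls. Stratify the Cox model for this comparison by propensity quintile, so that its hazard ratio carries the same adjustment as the log-rank test.
- Use that hazard ratio and its confidence interval as the estimate of comparator bias, and require it to be reviewed before any pooling. State that placebo subjects who start commercial OCA may shift it.
- If the pooled analysis is ever used, report OCA against randomized placebo alone on the same endpoint beside it.
- Reconcile 5.5.2.3 with the pooled analysis, and give one eligibility rule for historical controls in 13.1.1.1 and 13.1.8, listing any criterion the databases cannot support.

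The cost is wording and one extra run of a method already planned. The downside is an added estimate that commercial OCA use may distort, so it needs careful reading.

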13.1.9. Handling of Dropouts or Missing Data

Subjects who discontinue investigational product are expected to continue in the study until study termination.

Missing data will be assumed to be missing at random. In order to determine the effect of missing data on the analysis, efficacy endpoints will be analyzed using different methods of imputation as described below. In addition, the same analyses for primary and key secondary endpoints based on ITT and PP populations will be performed to assess robustness of analysis results. During the conduct of the study, the DMC may recommend refining the missing data strategy to better address the observed pattern of missing data, based on blinded monitoring of the data.

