13.1.12. Continuous Monitoring and Interim Analyses

Blinded safety reports including the accrual of events, drop outs, and/or loss of subjects to commercially available OCA will be reviewed by the DMC on a regular basis.

Two planned interim analyses of the liver-related outcomes will be conducted using the Lan-DeMets O'Brien-Fleming boundaries ([Reboussin 2000](#)). Both interim analyses will be pre-specified and will occur after accrual of 50% (64 events) and 75% (96 events) of clinical outcome events, respectively.

The DMC will review the available efficacy data in conjunction with detailed safety data and other relevant information to recommend continuation, modification, or cessation (for efficacy)

of the study beyond each interim analysis. Modification of the study would not take place without prior agreement with regulatory authorities.

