13.3. Data Monitoring Committee

An independent DMC that includes hepatologists, pharmaceutical physicians, epidemiology/cardiology expert(s), and statistician(s) not involved in the study as Investigators, adjudication committee members, or consultants. The DMC will have oversight over the study

conduct as defined by the DMC charter. All members will have considerable experience with clinical study conduct and DMCs. Any candidate found to have a conflict of interest or whose name is listed on the FDA debarment list will not be offered membership. Conflicts of interest will be assessed regularly, and if members are found to have a new conflict of interest they will be replaced.

The DMC will meet approximately quarterly at scheduled meetings and ad hoc meetings will be convened, as appropriate, to review safety and efficacy data in order to ensure the safe and proper treatment of subjects. Based on review of these data, the DMC will advise the Sponsor on the validity and scientific merit of continuing the study.

Written minutes of both the open and closed DMC sessions will be prepared. The closed minutes will be made available to the appointed Sponsor representatives only after the database is locked.

Data listings provided to the DMC do not contain individual subject treatment information; however, the DMC will have access to the database and may unblind individual subject data as appropriate. Summary tables reviewed by the DMC during closed sessions will include an overall column containing information regarding all subjects and separate treatment columns with 'dummy' labels, ie, the actual treatment groups are used, but are not identified. Data reviewed during the meetings will include, at a minimum, disposition, demographics, exposure, clinical laboratory results, Medical Dictionary for Regulatory Activities (MedDRA) coded AEs, and AEs leading to early withdrawal of investigational product. At each meeting, detailed narratives of interval SAEs (including events resulting in death) are reviewed by the DMC in addition to a cumulative list of all SAEs.

The DMC may agree to adjust meeting frequency based upon actual and projected safety and efficacy data availability. Adjustments to or stopping of the protocol defined doses may be considered based on DMC evaluation of OCA safety and tolerability.

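### Section 13.1.9 lets the DMC recommend refining the missing-data strategy on the basis of blinded monitoring, but the same DMC sees by-arm data and interim efficacy, so the recommendation cannot be assured to be independent of the treatment effect

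*Protocol*

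**What the plan says.** Section 13.1.9 assumes that missing data are missing at random and lists the handling rules. It adds that, while the study runs, "the DMC may recommend refining the missing data strategy to better address the observed pattern of missing data", and ties this to monitoring of the data in blinded form.

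Other sections describe what the DMC sees:

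- **Section 13.3.** Closed-session summary tables have an overall column and separate treatment columns under dummy labels: "ie, the actual treatment groups are used, but are not identified". The listings carry no individual treatment codes, but "the DMC will have access to the database and may unblind individual subject data as appropriate". The committee meets about quarterly to review safety and efficacy data.
- **Section 9.4.1.** The DMC has IWRS access and can unblind individual subjects.
- **Section 13.1.12.** Two efficacy interims, at 64 and 96 events, use Lan-DeMets O'Brien-Fleming boundaries. "The DMC will review the available efficacy data in conjunction with detailed safety data" and may recommend continuing, modifying or stopping for efficacy. The same section gives the DMC blinded reports on event accrual, drop-outs and loss to commercial OCA.

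Two sections limit what can follow. Under Section 13.1.8 the planned primary analysis is not revised without prior regulatory agreement. Under Section 13.1.12 the same condition applies to modification of the study.

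**The concern.** A mid-study change to missing-data rules is harmless to the type I error when those proposing it cannot know which choice helps which arm. Section 13.1.9 relies on that condition but gives the role to the one committee in the trial that may know the comparison. It names no separate blinded group and sets no cut-off such as the first interim.

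The protocol applies the right standard elsewhere. Sample-size monitoring (Section 13.1.2.1) uses pooled events without knowledge of comparative efficacy. Propensity modelling (Section 13.1.8) is done by third-party statisticians separate from those who run the efficacy analyses. Missing-data handling has no such separation.

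At stake is the pre-specification of the confirmatory tests: the primary log-rank test and the four key secondary endpoints. For bilirubin and ALP at end of study, which use ANCOVA on observed cases with imputation as sensitivity analysis (Section 13.1.9.2), the missing-data rule bears directly on the result. The alpha-spending boundaries cover repeated looks. They do not cover a choice of method made after a look.

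**Working it through.** **1. The design figures are not in dispute.** Section 13.1.2 gives: "The 2 groups will be compared using a 2-sided log rank test at the 5% level of significance"; "Exponential survival curves, placebo survival estimate of 0.6 at 8 years with a hazard ratio of 0.60"; "allowing for 4 years of subject accrual and 6 years of follow up"; 1:1 allocation; 10% dropout; and "a total of 127 events (both groups combined) will provide 80% power".

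- Schoenfeld, fixed design: 4(1.960 + 0.842)² / (ln 0.6)² = 120.3, so 121 events.
- Freedman, fixed design: (1.960 + 0.842)² × (1.6/0.4)² = 125.6, so 126 events. With the group-sequential inflation of 1.018 this becomes 127.9, so 128.
- Placebo hazard: −ln(0.6)/8 = 0.0639 per year. OCA hazard: 0.6 × 0.0639 = 0.0383. With uniform accrual the event probabilities are 0.398 and 0.263, mean 0.331. Then 127/0.331 ≈ 384 and 384/0.90 ≈ 427.

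The stated 127 events and 428 subjects therefore reproduce.

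**2. The passages side by side.** An efficacy boundary can be applied only to a between-arm statistic whose direction is known. After 64 events, then, the DMC knows the comparison whatever the column labels say. The blinded drop-out reports go to the same people. The statement of blinded monitoring in 13.1.9 and the DMC's access under 9.4.1, 13.1.12 and 13.3 cannot both guarantee an uninformed recommendation.

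**3. Illustration of size.** These are assumptions, not protocol figures. Take no treatment effect and two candidate strategies A and B, whose test statistics have correlation r. At information fraction t the strategy with the result more favourable to OCA is picked. It is then tested once at the end against 1.96 (the interim stopping rule is ignored).

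The final statistic for A has correlation c = √t × √((1 − r)/2) with the standardised difference A − B at time t. By symmetry, the one-sided error is 2 × P(Z > 1.96, D > 0), where Z and D are standard normal with correlation c.

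| Pick made at | r = 0.98 | r = 0.95 | r = 0.90 |
|---|---|---|---|
| t = 0.50 | 0.028 | 0.030 | 0.032 |
| t = 0.75 | 0.029 | 0.031 | 0.034 |
| t = 1 (final data) | 0.030 | 0.032 | 0.035 |

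The nominal value is 0.025. For example, t = 0.5 and r = 0.90 give c = 0.707 × 0.224 = 0.158 and an error of 0.032.

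**4. Are these correlations plausible?** A simulation with HR = 1, 428 subjects, a common hazard of 0.051 (about the mean of 0.0639 and 0.0383), 4 years of accrual and a 10-year end compared two rules: censor at dropout, or count dropout as an event. The correlation was 0.94, 0.89 and 0.80 at 5%, 10% and 20% dropout. Picking the better result on final data gave 0.033, 0.036 and 0.038. At the protocol's 10% dropout this agrees with the bottom right of the table. Counting every dropout as an event is an extreme alternative, so closer rules would give higher correlations and smaller inflation.

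**The case against.** The strongest reply is that the protocol has limits of its own.

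- The DMC recommends; it does not decide. Section 13.3 speaks of decisions made by the sponsor on DMC recommendations.
- Regulatory agreement is required before the planned primary analysis is revised (13.1.8) or the study modified (13.1.12).
- Section 13.1.12 does supply the DMC with blinded reports on drop-outs and loss to commercial OCA, which are the data a missing-data review needs. Section 13.1.9 ties the recommendation to the pattern of missing data, not to efficacy.
- Section 13 requires the SAP to be approved before the first interim.

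All of this stands, and it reduces the risk to the primary test considerably. It does not remove the conflict. Regulatory agreement limits implementation without making the recommendation blind, is not repeated in 13.1.9, and does not expressly reach missing-data rules for the key secondary endpoints. SAP approval before the first interim is undercut by a sentence that allows refinement at any time during the study.

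Stronger readings that a reader might infer are not supported:

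- *The DMC can change the analysis, so the type I error is no longer 5%.* It can only recommend, and the conditions above apply.
- *The two-sided error rises to 0.059–0.070 or more.* That counts picking the more extreme result in either direction on final data. Success under Section 13.1.10 requires significance in favour of OCA. When the pick always favours OCA, the two-sided rate stays at 0.050 and the error moves into the OCA tail.
- *Pruritus would reveal the arm behind the dummy labels.* Section 5.5.2.1 gives 56% versus 69% for two OCA regimens and no placebo rate.
- *Subjects who start commercial OCA or move to telephone contact are missing data.* Under Sections 8.4.1 and 9.7.15 they remain under follow-up.

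**Conclusion.** The point holds as an internal contradiction with limited consequences. Section 13.1.9 states a safeguard, blinded monitoring, that the protocol's own description of the DMC does not secure. A DMC recommendation on missing data therefore cannot be assured to be independent of the treatment effect.

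For two candidate strategies with assumed correlation 0.98 to 0.90, one-sided error rises from 0.025 to 0.028–0.034 if the choice is made at 50–75% information, and to at most 0.030–0.035 if made on final data. These figures assume a deliberate choice in favour of OCA that the sponsor and, for the primary analysis, regulators then accept. They show the scale of the exposure and are not a prediction. No sample-size or alpha figure changes. The correction is worth making because it costs little and protects the confirmatory tests.

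**What to change.** Replace the sentence in Section 13.1.9 with a rule along these lines: any refinement of the missing-data strategy is made by the sponsor's blinded statisticians from pooled, not by-arm, data, and is fixed in the SAP before the first interim analysis (64 events). This matches the SAP approval timing already stated in Section 13. Proposals made later, including any from the DMC, enter only as sensitivity analyses.

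Limit the restriction on the DMC to missing-data handling and cross-refer to Section 13.1.8. A blanket bar on DMC involvement in analysis methods would contradict that section, which allows the DMC to recommend a revised primary analysis after the interims, subject to regulatory agreement. Add a matching line to the DMC charter.

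The cost is one paragraph and one charter line. The downside is that insights gained after the first interim cannot alter the confirmatory analysis.
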